#### Analysis for Specific Aim 1b

Metabolite concentrations will be log-2 transformed, and associations between baseline metabolite concentrations and the time of abstinence since baseline will be evaluated by linear regression with age and gender as covariates. If Timeline Follow Back (TLFB) data at 3-months is absent, the date of last contact will serve as the day of first lapse unless the subject has reported a lapse at an earlier time point. To study the possible effect of depression severity and liver function, regression models including baseline PHQ-9 scores and LFTs (AST, ALT, and GGT) will be compared with those without to determine whether the metabolites remain significantly correlated with treatment outcome. Participants who provided paired blood samples will be classified as responders (maintenance of complete abstinence) or non-responders (any consumption of alcoholic beverages during the trial period), and their metabolite concentrations at baseline and at 3 months will be compared by two-way ANOVA to detect any significant changes between the two time points and whether these changes differ significantly between groups.

After metabolomic markers associated with length of sobriety (or additional secondary phenotypes) are identified, we will apply a “pharmacometabolomics-informed pharmacogenomics” research strategy. Specifically, we will perform genome-wide association analyses to search for genetic variants associated with metabolites that are associated with acamprosate clinical outcomes. We will then evaluate the association of the identified genetic variants ( $p < 5 \times 10^{-8}$ ) with clinical treatment outcomes in all available datasets (including the COMBINE and PREDICT datasets used in Aim 1a). We will also pursue all signals, genes and pathways functionally and mechanistically in order to investigate the biological mechanisms underlying sobriety length and other phenotypes associated with acamprosate treatment response. This is the same approach that we used previously with success to study biological mechanisms contributing to effects of selective serotonin reuptake inhibitors in patients with major depressive disorder (MDD).

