#### Analysis for Specific Aim 2a

Genetic association analyses will evaluate the effect of SNP genotypes on acamprosate and placebo treatment outcomes. Well-established pipelines will be used for genotype quality control and imputation prior to performing the genetic association analyses. We will first perform genome-wide association analyses of the primary outcomes in the acamprosate-treated participants with available 3 month outcomes, using standard approaches. For example, we will evaluate the association of SNPs with 3 month continuous abstinence (yes/no) using logistic regression and with length of abstinence using Cox proportional hazard models. We will first use these models to evaluate the association of the treatment outcomes with covariates, including demographic and baseline clinical characteristics, such as depression and anxiety symptom severity (PHQ-9 and GAD-7 scores, respectively), and liver function tests (LFTs) – aspartate aminotransferase (AST), alanine transaminase (ALT) and Gamma-Glutamyltransferase (GGT). SNP association with the primary treatment outcomes will be evaluated while adjusting for relevant covariates and principal components derived from genome-wide SNP data to adjust for population stratification. As discussed in the Statistics Team Section, secondary analyses will also be performed using the entire sample of participants enrolled into the study [“intent-to-treat” (ITT) analysis]. If the same genetic variants contribute to lack of response in the “completer” group and to early dropout (which is likely the case as early dropout frequently results from relapse), the ITT analysis will have greater power than the “completer” analysis. We will also perform genome-wide association analyses using all participants (acamprosate and placebo), including a treatment covariate, and a SNP-treatment interaction to evaluate whether SNPs are associated with clinical outcomes in a drug-dependent manner (e.g. SNP is associated with acamprosate treatment outcome, but not placebo treatment outcome). We will

also evaluate the possibility of sex-specific genetic effects, or genetic effects that are modified by the presence of comorbidities such as depression and anxiety, by exploratory analyses involving interaction terms with these variables.

Most importantly, we will perform a genome-wide meta-analysis of acamprosate pharmacogenomics using the new data and data from available prior studies (COMBINE, PREDICT, CITA; see Aim 1).

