Table 2 Subject Characteristics	COMBINE	PREDICT	CITA
N	1393	426	443
Age, mean(SD)	44.4 (10.2)	45.3 (8.7)	42.1 (11.8)
Sex, N(%) male	955 (69%)	328 (77%)	286 (65%)
Race, N(%) white non-Hispanic	1062 (77%)	426 (100%)	412 (93%)
Baseline Consumption Measures (last 30 days)			
Average drinks per drinking day	13.0 (8.1)	19.4 (11.3)	11.8 (7.7)
% drinking days	72.8 (23.5)	82.1 (1.3)	50.7 (29.7)
% heavy drinking days	65.2 (24.9)	79.0 (1.3)	45.8 (29.7)
Number of days since last drink	7.7 (5.3)	22.1 (4.4)	24.8 (16.1)
Medications			
Acamprosate, N	608	172	443
Naltrexone, N	614	169	0
No active drug (placebo or no medication), N	466	85	0
Treatment outcomes			
3 month abstinence from any drinking, N(%)	293 (21.2)	194 (45.5)	132 (29.7)
3 month abstinence from heavy drinking, N(%)	432 (31.2)	210 (49.3)	168 (37.9)

For COMBINE and CITA, baseline consumption is based on 30 days prior to the start of medication, while for PREDICT it is based on 30 days prior to the onset of inpatient treatment, as proposed by Mann and colleagues (84).

For the COMBINE study, the number of participants for each medication may include participants on more than one medication (i.e. groups are not mutually exclusive since the study included acamprosate/naltrexone co-treatment).

Numbers for treatment outcomes are based on the ITT sample (i.e. complete sample) assuming those who dropped out prior to 3 months had returned to heavy drinking.

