As with the analysis described above, our meta-analyses will also include analyses of the full set of acamprosate and placebo treated participants, with a treatment covariate and tests of SNP-treatment interaction effects. However, our power estimate for the meta-analysis is based only on the combined sample of acamprosate-treated patients, since the size of this sample will determine the power to detect acamprosate-specific pharmacogenomics effects. Assuming a total sample of 1000 acamprosate-treated participants (ITT), the meta-analysis will provide 80% power to detect associations of SNPs with 3-month abstinence during acamprosate treatment (assume ~1/3 abstain and 2/3 relapse) with odds ratios of 2.07 and 1.80 for SNPs with minor allele frequencies (MAFs) of 0.2 and 0.4, respectively, at a genome-wide significance level of  $5 \times 10^{-8}$ . We also note that analyses of the full dataset (N≈1500) including participants that received acamprosate or other treatment options will provide greater power to detect genetic predictors of treatment-independent predictors of abstinence in patients with AUD.

We recognize that the available sample has relatively little power to detect the effects of individual SNPs, which tend to be very modest for complex traits such as alcohol-dependence related phenotypes. We will therefore apply more advanced analysis methods to maximize power of the study, including gene-level and pathway-based (gene-set) analyses using approaches such as MAGMA [42], and will evaluate polygenic risk score associations and AUD treatment outcomes.

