### **Endpoints:**

The primary treatment outcome will be defined as continuous sobriety (yes/no) during 3 months of treatment.

Secondary outcomes (also assessed during 3 months of treatment) will include:

- (1) The number of days until first alcohol use assessed by TLFB.
- (2) Number of days until first relapse ( $\geq 5$  drinks/day for men and  $\geq 4$  drinks/day for women) will be assessed using TLFB.
- (3) Cumulative abstinence duration proportion: the proportion of days over the length of follow-up during which participants were completely abstinent from alcohol use, a score range of 0 (drinking continuously) to 100 (maintain complete abstinence) is applied.

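### Baseline drinking is available for all four cohorts but named in no outcome model, so its use, and uniform adjustment across the meta-analysis, is left to an undefined covariate step

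*Combined protocol and SAP*

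**What the plan says.** All references are to the combined protocol and SAP.

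- **Endpoints.** "The primary treatment outcome will be defined as continuous sobriety (yes/no) during 3 months of treatment". The three secondary outcomes are days to first drink, days to first heavy-drinking relapse, and the proportion of days abstinent.
- **Baseline data.** Table 1 schedules TLFB, with the BDQ as substitute, at baseline and months 1, 2 and 3. Table 2 has a block headed "Baseline Consumption Measures (last 30 days") for COMBINE, PREDICT and CITA. It covers drinks per drinking day, % drinking days, % heavy drinking days and days since last drink.
- **Aim 2a models.** Covariates are first examined against outcome. Those named are demographics and "baseline clinical characteristics, such as depression and anxiety symptom severity (PHQ-9 and GAD-7 scores, respectively), and liver function tests (LFTs": AST, ALT, GGT). The SNP test then adjusts for *relevant* covariates and ancestry components. No criterion for relevance is given.
- **Aim 1b model.** Metabolite associations with time abstinent are "evaluated by linear regression with age and gender as covariates". A comparison model adds PHQ-9 and liver tests. Aim 2b uses a similar strategy.
- **Power.** The claim is that "the meta-analysis will provide 80% power to detect associations of SNPs with 3-month abstinence during acamprosate treatment" at odds ratios of 2.07 (MAF 0.2) and 1.80 (MAF 0.4), with significance set at 5 × 10⁻⁸. The sample size behind it is itself an assumption: "Assuming a total sample of 1000 acamprosate-treated participants (ITT").

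**The concern.** The baseline value of an outcome is a natural covariate to fix in advance. Here it is either already collected or scheduled, but whether it enters any model depends on a relevance judgement that the plan does not define.

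Two things are at stake. First, the plan treats the four-cohort meta-analysis as its most important genetic analysis, and nothing requires the same adjustment set in each cohort. Log odds ratios conditional on different covariates could then be pooled. Second, the plan concedes little power for single SNPs. At a threshold of 5 × 10⁻⁸, an independent prognostic covariate brings some power for little cost.

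**Working it through.** **1. Which models name baseline drinking**

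| Analysis | Covariates named | Baseline drinking |
|---|---|---|
| Aim 1a heritability | study, ancestry components | no |
| Aim 1b metabolites | age, gender; comparison model adds PHQ-9, AST, ALT, GGT | no |
| Aim 2a SNP models | demographics, PHQ-9, GAD-7, AST, ALT, GGT (open list); ancestry components | not named, not excluded |
| Meta-analysis | treatment, SNP-by-treatment | no |
| Aim 2b metabolites | as Aim 1b, plus drug interaction | no |

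**2. The plan's 80%**

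Inputs from the Aim 2a section: N = 1000, α = 5 × 10⁻⁸ (two-sided assumed), the two OR/MAF pairs, and "assume ~1/3 abstain and 2/3 relapse". Method: per-allele logistic model, Hardy-Weinberg proportions, 1-df likelihood-ratio test.

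- With 1/3 as the abstinence risk in non-carriers, power is 81.7% (OR 2.07) and 80.0% (OR 1.80). The stated figure reproduces.
- With 1/3 as the overall abstinence rate, power is 78.2% and 71.4%.

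The gain below is anchored at the stated 80%, so that it does not depend on which reading was meant.

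**3. Gain from a fixed baseline covariate**

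For a covariate independent of genotype, the effective sample size is about N/(1 − R²). R² is the extra outcome variance explained, on the probability scale, beyond the covariates already in the model. With z(α/2) = 5.451 and z(0.80) = 0.842, which sum to 6.293:

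power = Φ(6.293/√(1 − R²) − 5.451); detectable OR = exp(√(1 − R²) × ln OR).

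Example at R² = 5%: 6.293/√0.95 = 6.456; 6.456 − 5.451 = 1.005; Φ(1.005) = 84.3%.

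| Incremental R² (assumed) | Effective N | Power | Detectable OR, MAF 0.2 / 0.4 |
|---|---|---|---|
| 0 | 1000 | 80.0% | 2.070 / 1.800 |
| 1% | 1010 | 80.9% | 2.062 / 1.795 |
| 2% | 1020 | 81.7% | 2.055 / 1.789 |
| 3% | 1031 | 82.6% | 2.047 / 1.784 |
| 5% | 1053 | 84.3% | 2.032 / 1.773 |
| 10% | 1111 | 88.1% | 1.994 / 1.747 |

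Reaching 85% needs R² of about 5.9%. For scale, at 1/3 abstinence an odds ratio of 1.2, 1.5 or 2.0 per SD of baseline drinking corresponds to R² of 0.7%, 3.4% or 9.0%.

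*Checks.* A simulation (4000 runs, OR 2.07, MAF 0.2, covariate OR 1.5 per SD) gave a squared z ratio of 1.033, against 1/(1 − 0.0344) = 1.036 predicted. From the lower bases of 78.2% and 71.4%, R² of 5% gives 82.6% and 76.5%, which is a similar gain of 4 to 5 points.

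**4. Is the measure comparable across cohorts?**

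- Table 2, footnote 1: the 30 days precede medication in COMBINE and CITA, but precede inpatient treatment in PREDICT.
- Table 2 prints an SD of 1.3 for PREDICT's % drinking days and % heavy drinking days, against 23.5 to 29.7 in the other two studies. With N = 426, 1.3 × √426 = 26.8, so the entry would fit a standard error. The documents do not say.
- CITA prints days since last drink as 24.8 (SD 16.1). If that is counted to the start of medication, a participant can have at most 31 − d drinking days in the 30-day window, where d is days since last drink. For any distribution with that mean and SD, the average of the positive part of 31 − d is at most ½[√(16.1² + 6.2²) + 6.2] = 11.7 days, or 39%. The printed mean is 50.7% drinking days. The two entries may therefore use different reference dates.
- In the new trial, entry requires 7 to 35 days without alcohol, the baseline TLFB look-back is not fixed, and the BDQ may replace TLFB.

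**The case against.** **The list is open.** The Aim 2a wording gives examples, and baseline drinking fits it. Elsewhere the plan intends to examine lifetime drinking history, craving and drug-taking situations as influences on outcome, and to include withdrawal severity in the analyses. This stands. A reader might infer that the plan omits baseline drinking and so gives up power, but the documents do not support that for Aim 2a. A reader might also infer a significance screen run separately in each dataset. No threshold and no such procedure is written; unequal adjustment is a possibility left open, not a stated step.

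**The size is assumed.** This also stands. No within-study association is given, and only the increment beyond GGT, PHQ-9 and the other covariates counts. Between studies the pattern is not a simple inverse: PREDICT has the heaviest drinking (19.4 drinks per drinking day) and the highest 3-month abstinence (45.5%). That comparison is confounded by study and says nothing about prognosis within one.

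**A SNP that only marks heavier drinking.** One might fear that such a SNP would surface as a response marker in the acamprosate-only analysis. The SNP-by-treatment tests and the placebo participants already address much of this. For such a SNP the gain computed above does not apply, and adjustment changes the quantity estimated.

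**What the objections leave.** No model names a collected baseline value of the outcome, relevance is undefined, and common adjustment across cohorts is not required.

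**Conclusion.** The point holds as a gap in prespecification with a modest, assumption-dependent cost. Baseline drinking is scheduled in the new trial and tabulated for the three prior studies, every endpoint is a drinking measure, and no outcome model names it. In Aim 2a its use is left to an undefined step; in the Aim 1b model that Aim 2b follows, it is absent.

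Anchored at the stated 80%, naming it would be worth about 1 to 4 points of power at an incremental R² of 1-5%, and about 8 points at 10%. This assumes a covariate independent of the SNP, two-sided α and N = 1000. A much larger gain might be inferred by assuming a correlation of 0.5 with abstinence, but that means 25% of outcome variance, and nothing in the documents supports it. The change would also not rescue the new sample alone, which the limitations section already calls unlikely to have sufficient power.

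**What to change.** In the Aim 2a section, and in the Aim 1b and 2b sections:

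1. Name one harmonised baseline drinking measure, for example log drinks per drinking day, or % heavy drinking days over a stated 30-day pre-treatment look-back. Make it a fixed covariate in the Aim 2a logistic, Cox, ITT and SNP-by-treatment models of every cohort, and in the Aim 2b metabolite models.
2. Define how other covariates are judged relevant, and require the same set in each cohort of the meta-analysis.
3. Before fixing the measure, check PREDICT's window and its printed SD of 1.3, and the reference dates behind CITA's entries. State the baseline TLFB look-back for the new trial.
4. State how participants with only a BDQ, or with no baseline value, are handled.
5. For genome-wide hits, also report the estimate without the covariate.

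Cost: a short addition to the text, one term per model, and some harmonisation and imputation work. No new visits or assays are needed. The adjusted SNP effect excludes any part acting through prior drinking, which is the reason for item 5.

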#### ***Recruitment process and infrastructure***

**Recruitment sites:** Patients will be recruited from study sites affiliated with the Mayo Clinic Addiction Services in the Rochester and Albert Lea campuses (Intensive Addiction treatment Program, Fountain Center Residential Treatment Program in Albert Lea, MN, Department of Psychiatry & Psychology Mayo Clinic Albert Lea) and Hazelden Betty Ford Foundation treatment Centers in Center City, MN and Plymouth, MN. Hazelden Betty Ford Foundation St. Paul location will be an alternative site to conduct study visits (no recruitment activities) to improve options for patient traveling while participating. With the integration of Rochester and the Health System sites into Mayo Midwest Department of Psychiatry & Psychology we have the ability to recruit at these campuses in the context of the integration and standardization of electronic medical records, nomenclature, clinical practices, and optimization of data capture, management and reporting. In addition, arrangements were made with the leadership of Hazelden Betty Ford Foundation allowing ensuring efficient enrollment process and data collection at the affiliated study sites. A brief description of each treatment program is presented below. Recruitment sites of Mayo Health System Albert Lea and Hazelden Betty Ford Foundation Treatment Centers (Center City & Plymouth) will rely on Mayo Clinic IRB and will be added when agreements are in place.

1. The Department of Psychiatry and Psychology at the Mayo Clinic in Rochester, MN has two treatment programs for persons 18 and older, which integrate a combination of psychosocial treatments with evidence-based pharmacotherapies of addiction under the direction of Board Certified addiction psychiatrists. The Intensive Addiction Program (IAP) is a 30-day residential treatment program that provides treatment 9 hours per day, 6.5 days per week, and the Outpatient Addiction Program (OAP) that provides an outpatient treatment program limited to 4 hours a day, 5 days per week. The combined annual census of the IAP and the OAP is 267 patients.

2. The Fountain Center Residential Treatment Program in Albert Lea, MN is a counselor-lead residential program for persons 18 and older with an emphasis on teaching relapse prevention skills. Fountain Center integrates the 12 Steps of Alcoholics Anonymous into the program. Annual census is 201 patients. Mayo has recently provided a shuttle service between Rochester and Albert Lea.

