### Study flow and Schedule of Events

Study personnel will explain the research risks and benefits. Written informed consent will be obtained for each study subject. The baseline diagnostic assessment, triage, treatment group assignment and follow up assessments are summarized in Fig. 1 and described in more detail in Specific Aim 2. Information regarding severity of alcohol withdrawal symptoms (measured by CIWA scale or site specific equivalent method) and medications used during withdrawal treatment preceding enrollment in the study will be collected or abstracted from the medical record and included in the data analyses.

\*Notation dated 5-12-2023: Upon IRB approval, subjects will no longer be randomized to the placebo arm. Instead, for the remainder of the study, all patients will be provided acamprosate to achieve the active drug and placebo ratio of 2:1.

Figure 1: Study Flow Chart

The presence of AUD and other psychiatric disorders will be confirmed by a computer version of the Psychiatric Research Interview for Substance and Mental Disorders (PRISM) [24]. The presence of comorbid depressive disorders requiring treatment will be determined by the combination of 2 characteristics: (1) the presence of any

diagnosis of depression during the previous year as confirmed by PRISM and verified by the study psychiatrist; and (2) a PHQ-9 score of 10 or above and/or a GAD-7 score of 10 or above. The interview will be conducted by interviewers trained and certified on the use of the PRISM. Interviewers, who have submitted required recordings and documents for certification and an unexpected delay in the certification process occurs, will be allowed to conduct prism assessment, if no other certified staff are available, with certification pending. The research pharmacy contracted for this study will randomize the study participants for all sites with placebo or acamprosate.

The schedule of study procedures and assessments is tabulated by visit in the Study Assessments in Table 1 (below). A visit window of +/- 10 days is allowed when scheduling. Questionnaires may be distributed in multiple formats (paper, electronic/mailed link, or asked/read to patient).

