### ***Study Medications:***

All participants will be randomized to receive acamprosate or placebo\* in a double-blinded placebo-controlled trial. Acamprosate, SSRIs, and SNRIs listed are FDA approved medications for the indications for which they are being used in this protocol; therefore the risk to participants is no more than that to the general population who may be taking these medications. Medication/Placebo\* administration starts with 1 pill 3 times a day for 7 days then increases to 2 pills 3 times a day.

\*Notation dated 5-12-2023: Upon IRB approval, subjects will no longer be randomized to the placebo arm. Instead, for the remainder of the study, all patients will be provided acamprosate to achieve the active drug and placebo ratio of 2:1.

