### Subject Information

Target accrual: 800 (400 Mayo Clinic; 400 Hazelden Addiction Treatment Centers)

Subject population: Adults (male and female)

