Other location's (Mayo Clinic Rochester & Hazelden Betty Ford, Center City, MN) patients' blood volume per blood draw: 50ml at Baseline (preferred but can be done at any visit) and 35 ml at Months 1 & 3

Hazelden Center City will offer participants to provide the additional ~15ml of blood as optional (preferred at baseline visit but can be done at any visit) for generation of the induced pluripotent stem cells (iPSCs) from peripheral blood mononuclear cells (PBMC) as described below.

Frequency of blood draw: three time points, Baseline, 1 and 3 month visits.

Blood samples for 35ml collection are for GGT levels: Serum Separator Tube (SST); DNA extraction, Acamprosate blood levels, Metabolomic, Proteomic biomarkers (EDTA tubes), and mRNA (PAXGene tube). The process of spinning and aliquoting the samples will be completed at each site. EDTA tubes that would need to be kept on ice, centrifuged in the cold (NOT frozen) with the plasma aliquoted into 200 ul aliquots which would need to be immediately placed and stored at minus 80 degrees. The current metabolomic platform would include both the amines and neuromodulators. Acamprosate blood drug levels will be plasma aliquoted into 300 ul aliquots and also assayed with these samples. PAXGene tube is placed directly into the minus 80 degree freezer.

An additional 15 ml of blood collected in EDTA tubes for peripheral blood mononuclear cells (PBMC) isolation. The separation and banking of PBMCs will be performed in the laboratory, frozen and stored in liquid nitrogen. PBMC are used to generate induced pluripotent stem cells (iPSCs), a cell type that can self-renew and which can be differentiated into many cell types from many human tissues.

## Review of medical records, images, specimens – Category 5

**For review of existing data:** provide a date range or an end date for when the data was generated. The end date can be the date this application was submitted to the IRB. Example: 01/01/1999 to 12/31/2015 or all records through mm/dd/yyyy.

**Date Range:** 12/29/2004 to 07/09/2013

Check all that apply (data includes medical records, images, specimens).

(5a) Only data that exists before the IRB submission date will be collected.

(5b) The study involves data that exist at the time of IRB submission **and** data that will be generated after IRB submission. Include this activity in the Methods section.

(5c) The study will use data that have been collected under another IRB protocol.

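### The Aim 2b metabolite models have no term for site or programme type, although plasma is processed locally and programmes differ, so a site difference could pass for a metabolite effect

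*Combined protocol and SAP*

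**What the plan says.** **Metabolite models.** Under Analysis for Specific Aim 1b, the association of baseline log-2 metabolite level with abstinence time "will be evaluated by linear regression with age and gender as covariates". Comparison models add PHQ-9 and liver function tests. Analysis for Specific Aim 2b adopts a similar strategy for the new cohort and adds an assessment of drug interaction. Neither section names site or programme type.

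**SNP models.** Under Analysis for Specific Aim 2a, "SNP association with the primary treatment outcomes will be evaluated while adjusting for relevant covariates and principal components derived from genome-wide SNP data". The candidate covariates are an open list of demographic and baseline clinical characteristics. The nearest existing term is study, which is a covariate in Aim 1a only.

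**Sample handling.** In the blood-collection text under Research Activity: "The process of spinning and aliquoting the samples will be completed at each site". A common instruction follows: "EDTA tubes that would need to be kept on ice, centrifuged in the cold (NOT frozen"), with immediate storage at minus 80 degrees.

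**Setting.** Under Recruitment process and infrastructure, "The Intensive Addiction Program (IAP) is a 30-day residential treatment program", and the same department also runs an outpatient programme. Of the other recruiting sites, one is a counsellor-led residential programme and the rest offer both residential and outpatient care. No other length of stay is given.

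**Entry and follow-up.** Inclusion requires 7 to 35 days without alcohol. The primary outcome is continuous sobriety during 3 months of treatment.

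**The concern.** Confounding by site needs two links: site must relate to the measured metabolite, and site must relate to relapse. The documents make both plausible. Local processing can shift measured levels, and different programmes can have different relapse rates. Age and gender block neither link.

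A false lead is also expensive here. Each selected metabolite goes on to a genome-wide association analysis, then to tests against clinical outcomes, then to functional work.

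There is a smaller, separate matter. Someone who enters the trial during a residential stay spends part of the 3 months in a setting that probably limits access to alcohol (an inference; the documents do not say so), whereas an outpatient does not. That makes the baseline hazard depend on setting.

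**Working it through.** The plan states no error rate, site difference or significance level for metabolites, so there is no figure of its own to reproduce. Its only power statement concerns SNPs in the meta-analysis and does not enter here.

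**Inputs from the documents**
- Sample: "Target accrual: 800 (400 Mayo Clinic; 400 Hazelden Addiction Treatment Centers"), taken as two equal site groups.
- Allocation: "all patients will be provided acamprosate to achieve the active drug and placebo ratio of 2:1". If 800 are enrolled and the ratio is reached, 800 × 2/3 ≈ 533 receive acamprosate.

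**Assumed inputs**
- A metabolite with no true effect, tested two-sided at 0.05.
- A shift d of 0.3 or 0.5 within-site SD between the two groups.
- Abstinence of 25% in one group and 35% or 40% in the other.

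**Step 1: induced correlation**
- r(site, metabolite) = (d/2) / √(1 + d²/4). This gives 0.148 for d = 0.3 and 0.243 for d = 0.5.
- r(site, outcome) = (Δp/2) / √(p̄(1 − p̄)). For 25% v 35% this is 0.05/√(0.30 × 0.70) = 0.109. For 25% v 40% it is 0.075/√(0.325 × 0.675) = 0.160.
- The spurious r is the product of the two.

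**Step 2: type I error**

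λ = √N × r, and the rejection rate is P(Z > 1.96 − λ) + P(Z < −1.96 − λ).

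| d (SD) | Abstinence | Spurious r | λ, N=800 | Type I error, N=800 | λ, N=533 | Type I error, N=533 |
|---|---|---|---|---|---|---|
| 0.3 | 25% v 35% | 0.0162 | 0.46 | 7.4% | 0.37 | 6.6% |
| 0.3 | 25% v 40% | 0.0238 | 0.67 | 10.3% | 0.55 | 8.5% |
| 0.5 | 25% v 35% | 0.0265 | 0.75 | 11.6% | 0.61 | 9.4% |
| 0.5 | 25% v 40% | 0.0388 | 1.10 | 19.6% | 0.90 | 14.6% |

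**Step 3: check by simulation**

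The formula uses yes/no abstinence, but the plan regresses abstinence time. A simulation (3,000 runs per scenario) of that regression with age and sex, N=800 and overall abstinence of one third gave:
- 0.25 SD and 10 points: 6% without a site term.
- 0.5 SD and 10 points: 11%.
- 0.5 SD and 20 points: 30%.
- Only one of the two site differences present: 4-5%.
- With a site term: 4.7-5.7% in all scenarios, including those with about 533 participants.

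**Step 4: the same path for SNPs**

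Site cannot change genotype, so bias needs a difference in allele frequency between sites that the ancestry principal components miss. The shift in z is √N × 0.25 × Δg × Δp / (SD_g × SD_y), where Δg is twice the residual allele-frequency difference.
- Extreme assumed case (frequency 0.2, residual difference 0.05, 20-point outcome gap, N=800): √800 × 0.25 × 0.10 × 0.20 / (0.566 × 0.471) = 0.53. The false-positive rate at the 5×10⁻⁸ level becomes 4.3×10⁻⁷.
- Residual difference of 0.01: 5.1×10⁻⁸ to 5.9×10⁻⁸.
- No residual difference: 5×10⁻⁸, unchanged.

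**Step 5: residential overlap with the 3-month clock**

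If the 30-day stay starts on the first sober day, the overlap is 30 minus the sober days at entry, and never below 0.
- Entry at day 7: 23 of 90 days (26%).
- Day 14: 16 (18%). Day 21: 9 (10%). Day 28: 2 (2%).
- Day 30 or later: 0.
- At the mean days since last drink in Table 2: 5.2 days (6%) for CITA (24.8) and 7.9 days (9%) for PREDICT (22.1).

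**The case against.** The strongest reply has five parts.

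- **Aim 2a excludes nothing.** This stands. Its covariate list is open, so site is unspecified there. A reader might infer that SNP associations are confounded by site. The documents do not support that: principal components are in the model, and the bias in Step 4 is small except under an extreme residual difference. A baseline hazard that depends on setting but not on genotype creates no false SNP signal either.

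- **Handling is standardised and findings are followed up.** This stands in part. The cold-handling instruction may shrink site shifts, but it does not adjust for what remains. Aim 2b uses the same platforms to replicate Aim 1b, and variants are then tested in other datasets, so an artefact would have to survive further steps. In the paired-sample comparison of baseline with month 3, a constant site offset cancels from the change. The exposed analysis is the regression on baseline level.

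- **A similar strategy need not mean identical covariates.** True, but the only metabolite covariates that the plan names are age and gender, with PHQ-9 and liver tests in comparison models.

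- **The sizes are assumed.** This stands. The 400/400 split is between two organisations, each of which offers both residential and outpatient care. It must not be read as residential against outpatient, and programme type alone does not justify a 10-15 point gap across it.

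- **The 23-day overlap is an extreme.** This stands. A reader might infer that a quarter of follow-up is protected. That needs entry on day 7 and admission on the first sober day, and only one programme has a stated length.

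A reader might also infer that the acamprosate-placebo contrast is confounded with site, because "The research pharmacy contracted for this study will randomize the study participants for all sites with placebo or acamprosate" with no stated stratification by site, and because placebo allocation later stopped. That would require the site mix to have changed over time, and the documents do not say that it did.

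**Conclusion.** The point holds for the Aim 2b metabolite models: site and programme type are not among the stated terms, and both links needed for confounding are plausible from the documents.

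Under the assumed shifts, the type I error for a null metabolite is about 7-20% with N=800 and about 7-15% with some 533 acamprosate-treated participants, against a nominal 5%. The lower end is close to nominal. These are not forecasts. They rest on two equal site groups, a two-sided 0.05 level and site differences in both metabolite and outcome, none of which the plan states apart from the 400/400 target. If only one difference is present, the error stays near 5%.

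For Aim 2a the omission is a matter of unspecified covariates and outcome noise, not of material SNP bias. Residential overlap ranges from 0 to at most about 23 days under the stated admission assumption.

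**What to change.** - **Aim 2b.** Add recruiting site (or processing site or batch, where that differs) and baseline programme type, residential or outpatient, as covariates in the metabolite and metabolite-by-drug models.
- **Aim 2a.** Name site and programme type among the relevant covariates in the logistic and interaction models, and use them as a stratum in the Cox model. State the purpose as reducing outcome noise.
- **Residential time.** Report the number of residential days after baseline as a range, and add a sensitivity analysis that accounts for them. Stratifying by programme does not remove variation in these days within a stratum.

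The cost is wording in the analysis section and a few degrees of freedom. Site and programme should be known at enrolment. The sensitivity analysis also needs the residential discharge date, which the documents do not list as collected.
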